9. STATISTICAL CONSIDERATIONS

9.1Primary outcome

Phase one:

- The proportion of participating staff adhering to the intervention (attending at least 4/6 sessions).
- The acceptability and perceived usefulness of the intervention established through focus group and qualitative interviews to inform revision of the intervention for the feasibility trial.

Phase two: The primary outcomes for the feasibility trial will be:

- The proportion of hostel staff participants adhering to intervention (attending at least 4/6 sessions)
- The proportion of participating staff completing candidate primary outcome for a full trial at follow up (SCIDS or MBI).

9.2Secondary outcome(s)

- The proportion of participating older people for whom primary outcome for the main trial is completed at follow up (EQ5D-5L / DADS).
- The estimated cost of delivering the intervention to inform their feasibility in a future full trial.
- The acceptability of and fidelity to the intervention established through a mixed methods process evaluation to assess intervention acceptability and required refinements.

9.3Sample size calculation

Phase two only: With 40 staff participants we will achieve the following 95% confidence interval for expected adherence and participation estimates:

1. Proportion of participants adhering to intervention (attending at least 4/6 group or individual sessions) (expected value 75%, 95% confidence interval: 59-87%).

2. Proportion of staff for whom potential staff outcomes (SCIDS or MBI) completed at 6-month followup (75%, 95% confidence interval = 59-87%).

With these numbers we will be able to estimate parameters with sufficient precision to inform continuation to an RCT. "Stop go" criteria will be related to intervention adherence:

- >=70%: go to main trial
- 60-69: modified trial to increase adherence
- <60: do not progress to main trial using this model.

This sample size will also be sufficient to estimate the standard deviation required for the sample size calculation in the main trial (43, 44).

9.4Planned recruitment rate

We estimate that recruitment referral rate will be approximately 10 potential staff participants month; 5 participants will be suitable and 4 will agree to participate and follow-up will be approximately 70%.

9.5Statistical analysis

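### Protocol section 9.3 plans 75% six-month SCIDS/MBI completion among staff, but section 9.4 expects only about 70% staff follow-up; the two planning values for this primary outcome need reconciling

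*Protocol*

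**What the plan says.** Section 9.1 names two primary outcomes for phase two. One is adherence. The other is "The proportion of participating staff completing candidate primary outcome for a full trial at follow up (SCIDS or MBI").

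Section 9.3 sets out the precision expected for both and opens with "With 40 staff participants we will achieve the following 95% confidence interval for expected adherence and participation estimates". Adherence is planned at "expected value 75%, 95% confidence interval: 59-87" per cent. Six-month completion has the same figures: "Proportion of staff for whom potential staff outcomes (SCIDS or MBI) completed at 6-month followup (75%, 95% confidence interval = 59-87" per cent. The stop/go thresholds in 9.3 apply to adherence only. The section closes its precision argument with: "This sample size will also be sufficient to estimate the standard deviation required for the sample size calculation in the main trial".

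Section 9.4 describes the expected monthly flow of potential staff participants: "5 participants will be suitable and 4 will agree to participate and follow-up will be approximately 70" per cent.

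Section 6.3.1 asks staff to complete both SCIDS and MBI, at baseline and at six months. Section 9.5.2 intends to obtain SDs and a correlation from these scores for the main trial's sample size calculation, and it refers further detail to a predefined analysis plan.

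**The concern.** Both figures describe staff at six months. Completing a six-month questionnaire requires being followed up, so the follow-up rate is a ceiling on the completion rate. A plan cannot expect 75% completion and about 70% follow-up in the same 40 people.

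The expected precision of a primary outcome is therefore stated on a value that the next subsection does not support. The same retention figure also decides how many staff will supply follow-up SDs and baseline-to-follow-up correlations, and section 9.3 refers only to the full sample when it calls the size sufficient for the SD.

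**Working it through.** **Inputs.** Staff sample n = 40 (section 9.3). Planned completion 75% with 95% interval 59-87% (section 9.3, item 2). Planned follow-up about 70% (section 9.4). Two-sided 95% confidence.

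**Step 1: reproduce the stated interval.** 75% of 40 is 30. The exact (Clopper-Pearson) limits for k of n are the 2.5% point of Beta(k, n−k+1) and the 97.5% point of Beta(k+1, n−k).
- k = 30, n = 40: 0.5880 and 0.8731, that is 58.8-87.3%, which rounds to 59-87%. The stated figure is reproduced.
- Other methods do not give both limits: Wilson 59.8-85.8%, Agresti-Coull 59.6-86.0%, Jeffreys 60.2-86.4%, Wald 61.6-88.4%.

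**Step 2: compare the two rates.** Completion = follow-up × completion among those followed up. With follow-up of 0.70, reaching 0.75 would need 0.75/0.70 = 1.07, more than everyone. If every person followed up completes, 0.70 × 40 = 28 complete, against the 30 planned.

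**Step 3: the interval at 70%.** For k = 28, n = 40 the exact limits are 0.5347 and 0.8344, that is 53-83%. The width is 83.44 − 53.47 = 30.0 percentage points, against 87.31 − 58.80 = 28.5 at 75%. The lower limit falls by about 5 points and the upper by about 4.

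**Step 4: precision of the SD.** For n independent, roughly normal scores, the 95% limits for the true SD, as multiples of the estimate, are √[(n−1)/χ²(0.975; n−1)] and √[(n−1)/χ²(0.025; n−1)]. Required main-trial size is proportional to the SD squared, so the squared upper limit shows how far it could be underestimated.

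| Staff contributing | Lower | Upper | Upper squared |
|---|---|---|---|
| 40 (baseline) | 0.82 | 1.28 | 1.65 |
| 30 (75% complete) | 0.80 | 1.34 | 1.81 |
| 28 (70% complete) | 0.79 | 1.36 | 1.85 |

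The conflict between the sections is the step from 30 to 28: 1.34 to 1.36 on the SD scale, 1.81 to 1.85 on the sample-size scale. The larger step from 40 to 30 is attrition that section 9.3 already implies by planning 75% completion.

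**The case against.** The strongest reply is that this is small and partly a matter of rounding. Section 9.4 says approximately, the difference is two people in 40, the interval hardly widens, the sample size of 40 is not derived from the completion rate, and no stop/go threshold uses completion. All of that stands, and it limits the weight of the point. It does not remove it: the figures sit in adjacent subsections, and one is a logical ceiling on the other.

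A reader might go further in four ways that the protocol does not support.

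- **That the 59-87% interval is miscalculated.** It is not; it is the exact interval for 30 of 40. What is in doubt is the 75% that goes into it, and the protocol does not show whether 75% or 70% is intended.
- **That the SD statement in 9.3 fails.** SCIDS and MBI are also collected at baseline, so an SD from all 40 staff will be available. Only follow-up SDs and baseline-to-follow-up correlations depend on completers. Setting 28 against 40 would charge ordinary, already planned attrition to the inconsistency.
- **That returning either questionnaire counts as completion, so that the outcome overstates each scale.** The wording is ambiguous, but no text says this. The outcome refers to a single candidate measure with two candidates in brackets. Both questionnaires are due at the same two time points, so they may well be missing together, and an analysis plan could settle the counting rule.
- **That the either-measure count could reach 30 of 40 while one scale lags.** This cannot be combined with 70% follow-up, under which at most 28 staff could return anything.

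**Conclusion.** The inconsistency is real and minor. Section 9.3 plans 30 of 40 staff completing at six months; section 9.4 allows at most about 28. The stated interval is right for 75% and would be 53-83% at 70%, an increase in width of 1.5 points. Neither the sample size nor the progression decision is affected.

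This rests on three assumptions: that the 70% in section 9.4 refers to the same consented staff as section 9.3, as its sentence suggests; that the completion denominator is all 40; and that staff are treated as independent, as the stated interval itself does. The wording of the SCIDS or MBI outcome is a point for clarification, not a defect shown by the protocol.

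**What to change.** Use one retention figure in sections 9.3 and 9.4.

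- If 70% stands, restate item 2 of section 9.3 as 70%, exact 95% CI 53-83% (28 of 40).
- If 75% stands, keep the interval and raise the follow-up figure in section 9.4 to at least 75%.
- In either case, add to the SD statement that baseline SDs can use all 40 staff, while follow-up SDs and baseline-to-follow-up correlations will rest on about 28 staff (about 30 if 75% stands).

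Optionally, say in sections 6.3.1, 9.1 and 9.3 that completion will be reported for SCIDS and for MBI separately. Section 3.2 wants a practical primary outcome confirmed for the main trial, and a combined count could not show which of the two is more practical.

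The cost is a few lines of text. The only downside, if 70% is chosen, is a slightly less favourable stated interval (30.0 against 28.5 points wide).

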9.5.1 Phase one

Assessment of outcomes

The proportion of eligible hostel staff approached who agreed to take part in the study will be reported with a 95% confidence interval and reasons for refusal summarised. Demographic characteristics of participating hostel staff will be summarised using means (with standard deviations (SD), medians (with interquartile ranges), counts and proportions, as appropriate.

Qualitative analysis of interviews

We will analyse the data thematically (45), inductively analysing interview data. We will check professional transcriptions against audio recordings and enter transcribed interviews into NVivo 12 software. We will code transcripts into meaningful fragments labelling initial codes. We will then organise data into preliminary themes responding to research questions and seeking connections. We will seek respondent validation, with Patient and Public Involvement (PPI) representatives to comment on the credibility of interpretations. Our findings will be used to adapt the HOME intervention and the supervision and training programme for facilitators delivering it if required before phase two. As the data will be collected by more than one researcher, PR will lead the analysis but each researcher will maintain their own reflective log and we will meet regularly to compare observations, explore differences and collaboratively and iteratively refine the analysis (46).

Assessment of fidelity to intervention

To analyse fidelity to the HOME intervention during delivery, checklists will be applied independently to transcribed audio recordings of the training sessions by two researchers. A mean fidelity score will be produced by dividing the number of items on the checklist identified as being delivered in the training sessions, by the number of items on the checklist that should have been delivered per training session, per facilitator and across all training sessions. We will adopt thresholds used in other intervention fidelity work: where 81–100% constitutes high fidelity, 51-80 is moderate fidelity and 50% or lower constitutes low fidelity.

9.5.2 Phase two

Assessment of outcomes

The statistical analyses will be described in a predefined analysis plan. The main analyses are: Baseline data will be summarised using means (with SD), medians (with interquartile ranges), counts and proportions, as appropriate, to describe characteristics. We will produce a consort diagram to describe the flow of participants through the trial and consider potential bias arising from dropouts and losses to follow-up.

1. We will calculate the proportion of staff adhering to the intervention (attending a predetermined number of sessions) with 95% confidence intervals.

2. The EQ-5D-5L, SCIDS and MBI scores will be summarised to provide distributional information and obtain estimates of SDs, and correlation needed for main trial's sample size calculation.

3. Referral rates, drop-out and loss to follow-up rates will be calculated with 95% confidence intervals.

4. Other staff and resident outcome data will be summarised using appropriate estimates with 95% confidence intervals.

Intervention costs

To calculate the unit costs of intervention delivery we will include: the hourly cost of training and supervising facilitators; hours spent by facilitators delivering training and supervision in hostels; hours spent by staff engaging in the intervention; capital travel and materials costs; and numbers of residents supported. We will obtain staff costs from published sources (47).

We will calculate service use for people with memory problems with data collected using the CSRI. Although previous research found only 15% of older UK hostel residents had monthly contact with family or friends (28), we will also collect information on informal support (via staff proxy) to inform the full trial. Unit costs from published sources (47) will be applied to each service for each participant and summed to give total service-related cost per participant in the three months before baseline and from baseline to six month follow-up. We will calculate summary statistics using means (with SDs) or medians (with interquartile ranges) across all participants for each service. Missed appointments will be costed as if the contact took place and the proportion of missed appointments reported. I will calculate unpaid care costs adapting existing methods (48); calculating replacement costs of equivalent number of hours of formal home care and applying a value for the hours of unpaid care equivalent to the national living wage (as we are unlikely to have details on informal carers to calculate more accurate costs).

Qualitative analysis of interviews

This will proceed as for phase one. Additionally, the evaluation will be informed by the Consolidated Framework for Implementation Research (CFIR)(49), a comprehensive tool to assess determinants of implementation. It includes considering how to adapt knowledge to local context, barriers to knowledge use and intervention tailoring. We will seek views on the potential impact of the intervention and any practice changes, as well as impacts on residents with memory problems. We will collate suggested changes to improve the intervention and future uptake and ask about experiences of completing outcome measures.

Measuring fidelity to intervention

This will proceed as for Phase one.

10. ASSESSMENT AND MANAGEMENT OF RISK

We do not think there are significant risks associated with the intervention or trial participation. intervention arm of the trial. The CI, study personnel and the trial management group will ensure that the study is conducted within appropriate NHS and professional ethical guidelines. Training and regular supervision will be provided to researchers on study procedures and intervention delivery by the CI.

The table below summarise the risks and mitigations:

| Intervention | Potential risk | Risk Management |
|--------------|----------------------|--|
| | Researcher safety | We are aware that hostels support individuals with complex mental health and substance misuse issues and we will follow local risk management procedures and liaise closely with hostel management when undertaking research activities in hostel settings. Researchers will be trained and will follow the UCL lone working policy which can be found on the UCL website: http://www.ucl.ac.uk/estates/safetynet/guidance/lone_workin g/lone_working.pdf At hostels, researchers will carry personal alarms and will follow local hostel safety procedures. Researchers will carry mobile phones and they will be able to contact the CI during work hours and out of hours. If the CI is unavailable (for example off sick or on holiday, researchers will contact a member of the study team after a hostel visit. The study team will have addresses, phone numbers and 'next of kin' details of all research assistants. |

| Psychological | Where this occurs during an assessment it will be mitigated by |
|---------------------------|--|

11.1 Definitions

| Term | Definition | | | | | | |
|-----------------------|--|--|--|--|--|--|--|
| Adverse Event (AE) | Any untoward medical occurrence in a patient or trial participant, which does not necessarily have a causal relationship with the intervention involved. | | | | | | |
| Serious Adverse Event | Any adverse event that: | | | | | | |
| (SAE). | • results in death, | | | | | | |
| | is life-threatening*, | | | | | | |
| | requires hospitalisation or prolongation of existing hospitalisation**, | | | | | | |
| | results in persistent or significant disability or incapacity, or | | | | | | |
| | • consists of a congenital anomaly or birth defect. | | | | | | |

| Other 'important medical events' may also be considered | | | | | |
|---|--|--|--|--|--|
| serious if they jeopardise the participant or require an intervention | | | | | |
| to prevent one of the above consequences | | | | | |

* A life- threatening event, this refers to an event in which the participant was at risk of death at the time of the event; it does not refer to an event which hypothetically might have caused death if it were more severe.

** Hospitalisation is defined as an in-patient admission, regardless of length of stay. Hospitalisation for pre-existing conditions, including elective procedures do not constitute an SAE.

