2. BACKGROUND AND RATIONALE

The older population experiencing homelessness and living with memory problems is growing (11, 12). Those experiencing homelessness have higher levels of cognitive impairment than those of equivalent age who have not (13-17) and are significantly more likely to have Alzheimer's disease and related dementias than stably housed populations (18, 19). The most deprived fifth of adults are 50% more likely to develop dementia than the fifth least deprived and live with its health and social care challenges (20, 21). People experiencing homelessness frequently have long-standing and interacting physical and mental health conditions, substance misuse (and Alcohol related brain damage) and history of traumatic brain injury (TBI) (22-24), undergoing accelerated ageing (16, 25-27) associated with increased service use and early death (15, 18).

There are few studies of dementia and memory problems in homeless people and these mainly consider prevalence (13), assessment and identification (14), with only one published intervention study and no RCTs. Prior to the HOME study there has been one recent non-interventional UK study on dementia and memory problems in people who are homeless, and we are building on their work in their study (28). Although studies suggest potential areas for intervention, only one Australian project evaluated potential solutions trialling a specialist residential model for older people with dementia linked to Alcohol Related Brain Damage (9). Their model included high staffing ratios, behaviour management, neuropsychological assessment, staff supervision, targeted activity and an individualised harm-minimisation approach to alcohol consumption. They compared seven residents with seven 'waitlist controls' over 18 months. After six months, compared to control group, residents displayed less challenging behaviour, reduced alcohol use, depression and anxiety and increased activity and QoL with reduced health and social care service use (9). This small, resource-intensive, non-randomised trial was the first attempt to evaluate an intervention in this population.

Little is known about how frontline staff provide support and how people with memory problems experience homelessness. Our recent qualitative study focused upon this and has shed light on the complex reality of support for older people experiencing homelessness and memory problems

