11.3 Procedures for recording and reporting Serious Adverse Events (SAEs)

All serious adverse events will be recorded in the CRF, and the sponsor's SAE log. The AE and SAE logs will be stored in the TMF and may be subject to Sponsor monitoring and auditing.

All SAEs (except those specified in the protocol as not requiring reporting to the Sponsor) will be reported to the Sponsor within 24 hours of becoming aware. The CI/PI or designated individual will complete the Sponsor's online Research Incident Reporting Form (https://redcap.slms.ucl.ac.uk/surveys/?s=NE5dypTdFo) within 24 hours of becoming aware of the event. The Chief or Principal Investigator will respond to any SAE queries raised by the Sponsor as soon as possible.

Where the SAE is unexpected and thought to be related to the intervention, this must be reported by the Investigator to the main REC that approved the study within 15 days of the Investigator becoming aware of the event, using the non-CTIMP safety report to REC form. This form can be found on the HRA website: https://www.hra.nhs.uk/approvals-amendments/managing-your-approval/safety-reporting/. The Sponsor should be copied into this, so they are aware. Discuss with the JRO Quality Assurance team in the first instance.

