11.4 Serious Adverse Events (SAEs) that do not require reporting (if applicable)

12.5 We will report any unexpected SAE to the study Sponsor. People experiencing homelessness frequently have long-standing and interacting physical and mental health conditions, substance misuse and history of TBI (22-24), undergoing accelerated ageing (16, 25-27) associated with increased service use and early death (15, 18). As such, the following events listed below describe expected disease related AEs that are not related to the trial intervention and we will not complete an SAE form and report it to the sponsor:

• For those experiencing homelessness and memory problems death, hospitalisation due to common causes related to their condition (e.g. Urinary tract infections, delirium, common infections, pneumonia) or transition to a care home as a result of progression of existing illness.

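### The SAE footnote in Protocol 11.1 excludes admissions for pre-existing conditions without separating planned admissions from acute worsening, and it overlaps inconsistently with 11.4

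*Protocol*

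**What the plan says.** Protocol 11.1 lists the seriousness criteria. One is an event that "requires hospitalisation or prolongation of existing hospitalisation". A double-asterisk footnote to that criterion first defines the term broadly ("Hospitalisation is defined as an in-patient admission, regardless of length of stay") and then narrows it: "Hospitalisation for pre-existing conditions, including elective procedures do not constitute an SAE".

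The other criteria carry no such exclusion. They include death, an event that "is life-threatening", persistent or significant disability or incapacity, and other important medical events, which may be considered "serious if they jeopardise the participant or require an intervention" to prevent one of the listed consequences.

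The sections that follow decide where an event goes:

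- **11.2 and 11.2.4:** every adverse event is assessed for severity, causality, seriousness and expectedness, and is recorded in the CRF and on the AE log.
- **11.3:** "All serious adverse events will be recorded in the CRF", and also in the SAE log. SAEs go to the sponsor within 24 hours unless the protocol exempts them. An SAE that is unexpected and thought related goes to the ethics committee within 15 days.
- **11.4:** under a heading about SAEs that need no reporting, it lists for residents death, "hospitalisation due to common causes related to their condition" (with urinary tract infection, delirium, common infections and pneumonia as examples) and transition to a care home. For these it waives the SAE form and the sponsor report.
- **12.1:** the trial management group's stated review items include SAEs. AEs are not named.

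**The concern.** An exclusion of this kind usually serves to keep planned treatment of an old problem from being counted as a new serious event. The footnote goes further. Because elective procedures are introduced only as an included example, an emergency admission for acute deterioration of a known illness is excluded on the same terms as a booked operation.

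That matters more in this trial than in most. Every resident is enrolled because of a recorded dementia diagnosis or a positive checklist screen for memory disorder (5.1). Section 2 adds: "People experiencing homelessness frequently have long-standing and interacting physical and mental health conditions". It also cites a mixed-methods study in which hostel residents with memory problems used more emergency and out-of-hours services than those without.

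The intervention changes how staff handle distress behaviour and harm minimisation (sessions 3 and 4 in 5.6). If it caused harm, acute worsening of a known condition is a plausible form for that harm to take. Oversight is light: 12.2 sets up no data monitoring committee, and section 14 sets no criteria for stopping early. Whether an event is classed as an SAE therefore largely decides who is required to look at it.

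**Working it through.** No formula applies: the plan states no figure here, and the question is how the definitions route an event. The check takes four kinds of resident admission through the sections as written.

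| Admission | SAE under 11.1? | CRF and AE log (11.2.4) | SAE log (11.3) | 11.4 |
|---|---|---|---|---|
| A. Planned, elective, known condition not worsened | No (footnote) | Only if it is an AE at all | No | Not relevant |
| B. Unplanned, acute worsening of a condition present at consent, no other criterion met | No (footnote) | Yes | No | Treats condition-related hospitalisation from common causes as an SAE without form or sponsor report |
| C. As B, but fatal, life-threatening, disabling or judged an important medical event | Yes (other criterion) | Yes | Yes | Waiver may apply |
| D. Unplanned, new acute infection | Yes (hospitalisation) | Yes | Yes | Form and sponsor report waived |

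**Step 1: scope of the footnote.** It is attached to the hospitalisation criterion alone, so it cannot remove row C. It has no qualifier for planned status or worsening, so it removes row B together with row A.

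**Step 2: what row B loses.** It keeps its CRF and AE log entry and its assessment under 11.2. Without SAE status it does not enter the SAE log and is not among the SAEs that 12.1 sends to the management group. It also cannot trigger the ethics-committee report in 11.3, which starts from an SAE that is unexpected and thought related. Where 11.4 would not have waived it, the 24-hour sponsor report is lost too. Section 11.2.2 says the differentiated causality assessment is captured on the SAE form, which row B would not have.

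**Step 3: 11.1 against 11.4.** The 11.4 waiver removes the form and the sponsor report, while 11.3 still requires the CRF and SAE log entry. If a row B admission falls within 11.4's condition-related hospitalisation, 11.3 and 11.4 together give: SAE, logged, not reported. The 11.1 footnote gives: not an SAE, not in the SAE log. For these admissions the sections give different answers. For row D they agree.

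**Step 4: who is affected.** Planned enrolment is 40 residents and 40 staff in phase two and up to 8 staff in phase one: 40 + 40 + 8 = 88. The footnote is not restricted to residents, but staff are not selected for illness. The effect therefore falls mainly on the 40 residents, who are 40/80 = 50% of phase two.

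**Step 5: how many events.** The protocol gives no admission rate, no share of admissions due to conditions present at consent, and no share of those that meet another criterion. The count cannot be derived.

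**The case against.** The strongest reply is that little is lost. Four parts of it stand, and each rules out a stronger inference that a reader might draw.

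- **That acute worsening can never be serious.** The text does not support this. The footnote touches one criterion only, so a fatal, life-threatening or disabling worsening, or one judged an important medical event, is still an SAE. An overdose, for example, could qualify by one of those routes. It may also be a new event with a known risk factor, and so not an admission for the pre-existing condition at all.
- **That the event disappears from the record.** It does not. Section 11.2.4 keeps every adverse event in the CRF and AE log, and 11.3 makes that log open to sponsor monitoring and audit. What changes is the classification and the routes that depend on it.
- **That a site cannot comply with both 11.1 and 11.4.** This goes too far. Section 11.4 still has work to do for deaths, which the footnote does not reach, and for acute new infections. It also describes its listed events as AEs, although its heading and the waiver of an SAE form treat them as SAEs. The inconsistency is confined to condition-related admissions where the condition pre-dates consent.
- **That a given share of admissions is lost.** Any percentage would be an assumption with no anchor in the protocol. Section 2 says such conditions are frequent and gives no proportion.

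It is also true that no SAE count is a primary or secondary outcome, that the stop-go rule in 9.3 rests on adherence, and that phase two has no comparator. The protocol does not say that the SAE count will feed into planning of the full trial.

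None of this answers row B. The important-medical-event criterion is discretionary, so it does not reliably recover such admissions. An AE log entry is also not the same as an item that the management group is charged with reviewing.

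**Conclusion.** The point holds in a limited form. The 11.1 footnote does not distinguish planned or stable admissions from acute worsening. For the 40 phase-two residents, an unplanned admission that is serious only through hospitalisation, and is for a condition present at consent, is therefore not classed as an SAE. It remains in the CRF and AE log but bypasses the SAE log, the management group's SAE review and the ethics-committee route. For the same admissions, 11.1 and 11.4 are not consistent.

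The direction is clear: the SAE count can only be lowered. The size is unknown and cannot be estimated from the protocol. The conclusion rests on reading the footnote literally. If the authors meant only planned admissions, the text does not say so. This does not block the study, but it should be corrected.

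**What to change.** Amend the 11.1 footnote so that it excludes only elective or pre-planned admissions for a condition present at consent that has not worsened. State that an unplanned admission for worsening of such a condition meets the hospitalisation criterion and is entered in the CRF and SAE log under 11.3.

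Reconcile 11.4 with that single definition, including whether its listed events are called AEs or SAEs. The waiver of the form and sponsor report in 11.4 may stay, so the extra work is mainly logging.

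The cost is about two sentences in a protocol amendment, more SAE log entries and a less favourable SAE count. The change affects how events are recorded and leaves participants' care untouched.
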